#### **10.4 Analysis of Vital Signs**

Vital sign measurements of systolic and diastolic blood pressure, pulse rate, respiratory rate, and body temperature will be summarized.

Each vital sign variable will be summarized for all time points (starting with Baseline) with the number of non-missing observations, mean and standard deviation, median, minimum and maximum. Mean change from baseline to each applicable post-baseline visit will be summarized for each vital sign variable, with the number of observations, baseline mean, and visit mean. The change from baseline mean, standard error, and 95%

confidence interval will be presented for the mean change from baseline within each treatment group and difference between treatment groups (ABBV-154 vs. Placebo).

Vital sign variables will be evaluated based on PCI criteria. Pulse rate, body temperature, and respiratory rate will follow the criteria in Appendix B. All other vital sign measurements will follow criteria in PSSAP. For each vital sign PCI criterion, the number and percentage of subjects who have a vital sign value meeting the criteria will be summarized. Listings will be provided to summarize subject-level vital sign data for subjects meeting PCI criteria.

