Glucocorticoids are highly effective at reducing inflammation and relieving pain. However, the administration of glucocorticoids is limited due to their long-term systemic side effect profile including (but not limited to) hypothalamic-pituitary-adrenal (HPA) axis suppression, increased rates of bone fracture due to osteoporosis, cardiovascular events, hyperglycemia, glaucoma, skin thinning, and weight gain. These adverse effects are generally dependent on dose, treatment time, concomitant and previous glucocorticoid intake, and individual sensitivity. Therefore, once initial remission is achieved, glucocorticoids should be tapered to minimize systemic side effects.⁶ Unfortunately, disease flares often occur while tapering glucocorticoids, resulting in long-term glucocorticoid-associated morbidity.

Recent studies in patients with rheumatoid arthritis (RA) on glucocorticoids illustrate significant risks to patients even when used at low doses. In a retrospective cohort study, adults with RA on low-dose glucocorticoids (5 mg/day or less) had a statistically significant increase in the risk of hospitalized infection, similar to that seen in patients on biologic therapies in other studies.⁷ A prospective cohort study of patients with RA with or without low-dose glucocorticoid treatment at least once during a follow-up period (median 10 years), showed patients with exposure to low-dose glucocorticoid experienced significantly more severe events (death, cardiovascular disease, severe infection, or

fracture). The median duration of low-dose glucocorticoid treatment was 44.6 +/-40.1 months, and there was a time-dependent relationship between glucocorticoid treatment and the increased risk of these severe events.⁸ In a population-based cohort analysis of 87,794 adults with six immune-mediated inflammatory diseases with no prior cardiovascular disease, including PMR patients (n = 25,581), the overall absolute risk of cardiovascular disease doubled after one year of using less than 5 mg prednisolone per day.⁹

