Such an event can result from use of the drug as stipulated in the protocol or labeling, as well as from "special situations" such as accidental or intentional overdose, medication error, occupational or accidental exposure, off-label use, drug abuse, drug misuse, or drug withdrawal, all which must be reported whether associated with an AE or not. Any worsening of a pre-existing condition or illness is considered an AE. Worsening in severity of a reported AE should be reported as a new AE. Laboratory abnormalities and changes in vital signs are considered to be AEs only if they result in discontinuation from the study, necessitate therapeutic medical intervention, meet protocol-specific criteria (see Section 6.2 regarding toxicity management), and/or if the investigator considers them to be AEs.

Since the primary endpoint for this study is time to PMR flare, these endpoint events (shoulder and/or hip girdle pain with inflammatory stiffness, neck pain with inflammatory stiffness, or new or worsened limited range of motion of hips and/or shoulders that are not due to other causes) will not be collected as AEs unless they fulfill criteria for an SAE or result in a fatal outcome. Expected manifestations of PMR that constitute worsening of the underlying condition are not to be recorded as AEs.

The investigators will monitor each subject for clinical and laboratory evidence of AEs on a routine basis throughout the study. All AEs will be followed to a satisfactory conclusion.

An elective surgery/procedure scheduled to occur during a study will not be considered an AE if the surgery/procedure is being performed for a pre-existing condition and/or the surgery/procedure has been preplanned prior to study entry. However, if the pre-existing condition deteriorates unexpectedly during the study (e.g., surgery performed earlier than planned), then the deterioration of the condition for which the elective surgery/procedure is being done will be considered an AE.

If any of the following events are reported, then the following supplemental report must be completed.

Event	Supplemental Report
Cardiac events Myocardial infarction or unstable angina Heart failure Cerebral vascular accident and transient ischemic attack Cardiovascular procedures (SAE Supplemental Procedure eCRF)	MACE eCRF
Discontinuation or interruption of study drug due to a hepatic-related AE A hepatic-related SAE Confirmed ALT or AST > 3 × ULN	Hepatic eCRF

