Dispense wearable device (substudy) ^c		✓	Subject wears the device and performs UL-ROM at home during the 1st hour after getting out of bed each day for 1 week after each site visit with UL-ROM assessment (Baseline and Weeks 4, 8, 12, 16, 20, 24, 28, 32, and 36 ^c)																			
Collect wearable device (substudy) (*Week 38 or 40; **If discontinuing all study participation)																		✓	✓*		✓	**
Dispense electronic patient-reported outcome (ePRO) handheld device		✓	Subject Completes Daily Diary for Pain and Stiffness Severity NRS; daily Day 1 - Week 52																			
Collect ePRO handheld device (*Week 52)																			✓*		✓	
LOCAL LABS & EXAMS																						
Body weight (*Weeks 36 and 52)	✓	✓				✓		✓		✓			✓		✓		✓		✓*		✓	✓

Activity	Screening	Baseline	Optional PK	Wk 1	Wk 2	Wk 4	Wk 6	Wk 8	Wk 10	Wk 12	Optional PK	Wk 14	Wk 16	Wk 18	Wk 20	Wk 22	Wk 24	Wks 26 – 52 ^a	Unscheduled for flare evaluation ^b	Premature Discontinuation	30-Day Follow-up Phone Call	70-Day Follow-up Visit
	Day -35 to Day 1	Day 1	Days 3, 4	Day 8	Day 15	Day 29	Day 43	Day 57	Day 71	Day 85	Days 87, 88, 92	Day 99	Day 113	Day 127	Day 141	Day 155	Day 169	EOW Visits				
Height	✓																					
Vital signs	✓	✓		✓	✓	✓		✓		✓			✓		✓		✓		✓		✓	✓
Physical exam	✓	✓								✓							✓		✓		✓	
12-lead electrocardiogram (*Week 52)	✓																✓		✓*		✓	
Chest x-ray	✓																					
Dual-energy x-ray absorptiometry scan (*Week 52)	✓																		✓*			
Assessment of PMR signs and symptoms		✓				✓		✓		✓			✓		✓		✓		✓	✓	✓	
Physician Global Assessment of Disease Activity NRS		✓				✓		✓		✓			✓		✓		✓		✓	✓	✓	
Elevation of upper limbs (EUL)		✓				✓		✓		✓			✓		✓		✓		✓	✓	✓	
Upper limbs range of motion (UL-ROM) and goniometer measurement (substudy) ^c		✓				✓		✓		✓			✓		✓		✓		✓	✓	✓	
Physician Assessment of Bruising Severity NRS (*Weeks 36 and 52)		✓								✓							✓		✓*		✓	
Photographic documentation of bruising (subjects who consent)		✓								✓							✓					
Erythrocyte sedimentation rate (ESR)	✓	✓				✓		✓		✓			✓		✓		✓		✓	✓	✓	

Activity	Screening	Baseline	Optional PK	Wk 1	Wk 2	Wk 4	Wk 6	Wk 8	Wk 10	Wk 12	Optional PK	Wk 14	Wk 16	Wk 18	Wk 20	Wk 22	Wk 24	Wks 26 – 52 ^a	Unscheduled for flare evaluation ^b	Premature Discontinuation	30-Day Follow-up Phone Call	70-Day Follow-up Visit
	Day -35 to Day 1	Day 1	Days 3, 4	Day 8	Day 15	Day 29	Day 43	Day 57	Day 71	Day 85	Days 87, 88, 92	Day 99	Day 113	Day 127	Day 141	Day 155	Day 169	EOW Visits				

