### **7.1 Demographics and Baseline Characteristics**

Continuous demographic variables include age, weight, height, and body mass index (BMI). Categorical demographic variables include sex, ethnicity, race, age Group 1 (< 65, or ≥ 65 years), age Group 2 (< 65, ≥ 65 and < 75, or ≥ 75 years), weight Group 1

(< 60 or ≥ 60 kg), weight Group 2 (< 100 or ≥ 100 kg), BMI Group 1 (< 25 or ≥ 25 kg/m^2), BMI Group 2 (< 35 or ≥ 35 kg/m^2), region (Europe, North America, or rest of world), tobacco user (current, former, never, unknown), and alcohol user (current, former, never, unknown).

Disease characteristics that will be summarized as continuous and categorical variables are listed below:

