## **10.6 Other Safety Analyses**

ECG is collected at screening, Week 24, and Week 52. ECG findings will be summarized by treatment group for each parameter and visit.

Dual-energy X-ray absorptiometry (DXA) is collected at screening and Week 52. DXA measurements, including bone mineral density and the corresponding T-scores and Z-scores, will be summarized by treatment group for each visit and also in the following subgroups:

- Vitamin D status at baseline ( $< 30$  and  $\geq 30$  nmol/L)
- Female patients' post-menopausal status at baseline (Yes and No)
- Bone protective agent status at baseline (Yes and No)

If available, body composition should be collected at screening and Week 52. Body composition measurements, including body fat mass (grams), lean body mass (grams), total body mass (grams), fat (%), and lean (%) will be summarized by treatment group for each visit.

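### SAP 10.4 leaves body weight out of its analysed variables, so change in scale weight by arm has no specified summary although it is scheduled at eight on-treatment visits

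*SAP*

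**What the plan says.** **Why weight is of interest.** The synopsis and Protocol 2.1 list the systemic harms of glucocorticoids, and the list in 2.1 ends with "hyperglycemia, glaucoma, skin thinning, and weight gain". Safety is part of the primary objective (Protocol 3.1). Protocol 6.1 includes systemic glucocorticoid side effects and iatrogenic Cushing's syndrome among the safety topics to be monitored.

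**What is collected.** Appendix F has a row whose label begins "Body weight (*Weeks 36 and 52", separate from the row for vital signs. It is ticked at Screening, Baseline, Weeks 4, 8, 12, 16, 20 and 24, Weeks 36 and 52, the Premature Discontinuation visit and the 70-day Follow-up Visit.

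**What is analysed.**
- SAP 10.4: "Vital sign measurements of systolic and diastolic blood pressure, pulse rate, respiratory rate, and body temperature will be summarized". Each of these variables gets descriptive statistics at every time point, mean change from baseline, and the difference between ABBV-154 and placebo with a 95% CI.
- SAP 10.4 on potentially clinically important (PCI) criteria: pulse, temperature and respiratory rate use Appendix B, and "All other vital sign measurements will follow criteria in PSSAP". Table B2 has no weight row.
- SAP 7.1 uses weight as a baseline descriptor: "Continuous demographic variables include age, weight, height, and body mass index (BMI".
- SAP 10.6: "If available, body composition should be collected at screening and Week 52". The summary covers fat mass, lean mass and "total body mass (grams), fat (%), and lean (%) will be summarized by treatment group for each visit".

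**The concern.** ABBV-154 is meant to let subjects stop systemic glucocorticoids and so avoid their harms, but its payload is itself a glucocorticoid receptor modulator. Weight could therefore move either way: down if steroid exposure is spared, or up if the payload acts systemically. Either result would bear on the safety half of the primary objective and on the comparison of doses.

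The protocol has subjects weighed repeatedly and treats the measurement as safety data: the summary of changes says body weight was added to the 70-day visit for more robust safety data collection. SAP 10.4 lists its variables by name and weight is not one of them. A programmer working from the SAP would produce weight at baseline and no table of its change by arm.

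SAP version 2.0 added criteria for HbA1c, HDL and LDL and more detail on bone mineral density. Weight, which the protocol names as a harm, was left without an equivalent.

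**Working it through.** The plan states no figure here to reproduce. The check is a count of scheduled weights, a search of the SAP for analyses that use them, and an indication of precision.

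**1. Scheduled on-treatment weights after baseline** (Appendix F, body-weight row): Weeks 4, 8, 12, 16, 20, 24, 36 and 52 = 8 visits. Week 52 is two weeks after the last dose at Week 50 but within the 52-week Treatment Period. Premature Discontinuation and the 70-day visit are not counted.

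**2. Planned values.** With 160 subjects, 8 × 160 = 1,280, or 8 × 40 = 320 per arm. This is a ceiling: it assumes every subject attends every visit.

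**3. Where the SAP uses weight or body mass.**

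| SAP section | Measure | After baseline? | Change or arm difference specified? |
|---|---|---|---|
| 7.1 | Scale weight, BMI | No | No |
| 10.4 | Five vital signs, not weight | Yes | Yes, but not for weight |
| 10.6 | Total body mass, if available | Week 52 only | No |
| Appendix B, Table B2 | Pulse, temperature, respiratory rate | Yes | No weight criterion |

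Specified analyses of scale weight after baseline: 0. Specified summaries of any body mass after baseline: 1, conditional, at one time point.

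**4. Precision that an added analysis would have.** For the difference in mean change between one dose and placebo, half-width = 1.96 × SD × √(2/n), with n = 40 per arm (Protocol 7.10). The documents give no SD of weight change, so a range of 3 to 5 kg is assumed.

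- SD 3 kg: 1.96 × 3 × √(2/40) = 1.31 kg
- SD 4 kg: 1.96 × 4 × √(2/40) = 1.75 kg
- SD 5 kg: 1.96 × 5 × √(2/40) = 2.19 kg

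With fewer evaluable subjects the half-width grows by √(40/n).

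**The case against.** **Body mass is summarised in SAP 10.6.** This stands, and it limits the point. A reader might infer that weight change is never reported at all. The documents do not support that: total body mass is tabulated by arm at Screening and Week 52 where body composition is available, which allows a before-and-after reading. It does not close the gap. It is conditional, has one time point after baseline and specifies no change or treatment difference. At the Primary Analysis, which waits only for the Week 24 visit, it could exist only for subjects who had already reached Week 52.

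**The PSSAP may cover weight.** It is not among the documents, so a PCI criterion for weight can be neither confirmed nor ruled out. But SAP 10.4 refers to it only for PCI criteria, not for visit summaries or mean change.

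**Adverse event reporting would pick up notable gain.** Partly so. Investigators can report weight gain as an adverse event, and potentially glucocorticoid-related events are adjudicated. A reader might infer that Protocol 6.1 closes this route, since "changes in vital signs are considered to be AEs only if they result in discontinuation from the study" or meet one of the other listed conditions. That argument is weak. If weight is not a vital sign, as its separate row suggests, the restriction does not reach it. If it is one, Protocol 7.5 already promises a summary of mean change in vital signs, and the SAP list is incomplete. On either reading, event counts do not measure a moderate shift in mean weight between arms.

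**No commitment is broken and nothing is lost.** Also fair. Weight change is not a listed safety measure in Protocol 3.5, and Protocol 2.2 does not name it among the items to be closely monitored. The weights would still be in the database, no test is biased, and they could be tabulated later. That lowers the weight of the point, but a prespecified table is more credible than one added after unblinding.

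**Conclusion.** The point holds as a gap in the SAP's specification. Scale weight is scheduled at eight on-treatment visits and bears on a harm that the protocol names, but the SAP specifies no summary of its change and no comparison with placebo. The only body-mass summary after baseline is the conditional Week 52 total body mass in 10.6.

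Its size is up to 1,280 planned weights, fewer with dropout. The half-width of about 1.3 to 2.2 kg rests on an assumed SD and on 40 evaluable subjects per arm. A reader might infer that a steroid-type gain would certainly show. The documents do not support that, because they state neither an expected gain nor an SD.

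This is an inexpensive completeness improvement to the safety analysis. It affects no efficacy result and calls for no change in how subjects are managed.

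**What to change.** Add body weight to the variable list in SAP 10.4, so that it receives the treatment already described there: summaries at each scheduled visit, mean change from Baseline, and the ABBV-154 minus placebo difference with a 95% CI, in the Safety Population. Do this before unblinding for the Primary Analysis.

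A categorical criterion for weight change in Table B2 is optional. The documents offer no basis for a particular cut-off, so the sponsor should choose one and check it against the PSSAP to avoid duplication or conflict.

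The cost is one variable added to a list and one more run of an existing table program. No new data, visits or assessments are needed.

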## **10.5 Safety Subgroup Analyses**

The AE Overview and AE by SOC and PT summaries will be provided for the following subgroups:

- Baseline Glucocorticoid dose Categories Group 1 ( $< 7.5$ ,  $\geq 7.5$  and  $< 10$ ,  $\geq 10$  and  $\leq 15$ , or  $> 15$  mg/day prednisone equivalent)
- Baseline Glucocorticoid dose Categories Group 2 ( $< 10$  and  $\geq 10$  mg/day prednisone equivalent)
- Duration of PMR Diagnosis Categories ( $< 1$ ,  $\geq 1$  and  $\leq 2$ , or  $> 2$  years)
- Length of prior glucocorticoid treatment for PMR ( $\leq 1$  and  $> 1$  year)

If any subgroup has fewer than 10% of the total subjects, then the analysis for this subgroup will not be performed.

## **10.6 Other Safety Analyses**

ECG is collected at screening, Week 24, and Week 52. ECG findings will be summarized by treatment group for each parameter and visit.

Dual-energy X-ray absorptiometry (DXA) is collected at screening and Week 52. DXA measurements, including bone mineral density and the corresponding T-scores and Z-scores, will be summarized by treatment group for each visit and also in the following subgroups:

- Vitamin D status at baseline ( $< 30$  and  $\geq 30$  nmol/L)
- Female patients' post-menopausal status at baseline (Yes and No)
- Bone protective agent status at baseline (Yes and No)

If available, body composition should be collected at screening and Week 52. Body composition measurements, including body fat mass (grams), lean body mass (grams), total body mass (grams), fat (%), and lean (%) will be summarized by treatment group for each visit.

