2.2 Benefits and Risks to Subjects

The clinical efficacy of glucocorticoids in the treatment of PMR is well established. By utilizing expression of transmembrane TNF on activated immune cells, ABBV-154 has the potential to deliver an anti-inflammatory payload intracellularly, while minimizing systemic exposure to the free payload GRM. Based on the preclinical data discussed in the ABBV-154 Investigator's Brochure, ABBV-154 is expected to demonstrate a positive benefit-risk profile for the treatment of PMR.¹⁴

Medical review of the safety data from the Phase 1, single ascending dose study did not identify any unexpected risk or trend in the healthy volunteer population (including Japanese and Chinese subjects). For further details, please see the ABBV-154 Investigator's Brochure.¹⁴

In clinical settings, TNF antagonists and glucocorticoids have been associated with increased risk for serious infections due to bacterial, mycobacterial, invasive fungal, viral, parasitic, or other opportunistic pathogens. Patients with a recent history of these events will be excluded from the study. Other known adverse events (AEs) associated with glucocorticoids include hypertension, HPA axis suppression, decreased bone formation, and cataract. Signs of infection, blood pressure changes, HPA axis function, and bone mineral density will be closely monitored during the study.

TNF antagonists have also been associated with an increased risk for serious allergic reactions, including anaphylaxis; infusion reactions; malignancy (including nonmelanoma skin cancer, lymphoma, and leukemia); worsening or new onset heart failure; and rarely hepatitis B virus (HBV) reactivation, central nervous system, demyelinating disease, pancytopenia (including aplastic anemia), and lupus-like syndrome. Patients with a history of these events will be excluded from the study. Signs and symptoms of these events will be closely monitored.

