Rationale: To collect additional data on subjects Baseline status which may affect bone mineral density.
- Protocol [Appendix F](#), Activity Schedule; Operations Manual Section 2.4, Individual Post-Treatment Period Visit Activities: Added PK and immunogenicity sample collection at the 70-day Follow-Up Visit.

Rationale: To ensure drug washout and assess immunogenicity during drug washout.
- Operations Manual, Section 1, Contacts: Updated Clinical Lab and Biomarker Sample Storage contact information.

Rationale: Administrative change.
- Operations Manual, Section 2.1, Individual Treatment Period Visit Activities: All individual study day headers were updated to include an additional column.

Rationale: Added for alignment with the 30-day phone call column in the Study Activity Table.
- Operations Manual, Section 2.1, Individual Treatment Period Visit Activities: For screening visit, changed reference for Section 3.6 to 3.5, describing chest x-ray.

Rationale: To correct typographical error.
- Operations Manual, Section 2.2 Premature Discontinuation Visit, Footnote b: Footnote was removed.

Rationale: Footnote was not applicable to the premature discontinuation visit anymore since subjects no longer wear the device continuously.
- Operations Manual Section 3.2, Rescreening: Added additional opportunity for rescreening of subjects with the AbbVie Therapeutic Area Medical Director/Scientific Director approval.

Rationale: To allow subjects who have already been screened twice the opportunity to rescreen on a case-by-case basis, if appropriate.
- Operations Manual Section 3.2, Rescreening: Added FSH to the list of testing not required to be repeated if rescreening a subject within 14 days from the sample collection date of the previous screen.

Rationale: To reduce unnecessary procedures, as FSH would not be expected to change significantly in 14 days.
- Operations Manual Section 3.6, Dual-Energy X-Ray Absorptiometry (DXA) Scan: Added collection of Z-score for evaluation of bone mineral density and instruction that measurements should be obtained from the distal forearm if the spine nor either hip are able to be scanned or

interpreted. Added a Central Imaging Core Lab for central independent review of DXA data and modified guidance for image acquisition.

Rationale: To improve the robustness and interpretability of the DXA data collected.

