### 10.3 Analysis of Laboratory Data

Data collected from central and local laboratories, including additional laboratory testing due to an SAE, will be used in all analyses, except for Baseline where SAE-related laboratory assessments on or before the first dose of study drug will be excluded. The clinical laboratory tests defined in the protocol operations manual (e.g., hematology and clinical chemistry) will be summarized.

Each laboratory variable will be summarized for all time points (starting with Baseline) with the number of non-missing observations, mean and standard deviation, median, minimum and maximum. Mean change from baseline to each applicable post-baseline visit will be summarized for selected laboratory variables, with the number of observations, baseline mean, and visit mean. The change from baseline mean, standard error, and 95% confidence interval will be presented for the mean change from baseline within each treatment group and difference between treatment groups (ABBV-154 vs. placebo).

Changes in laboratory parameters will be tabulated using shift tables either by NCI CTC criteria or categorized as low, normal, or high based on the normal ranges of the laboratory used for each sample. A shift table from baseline either to the worse value (based on NCI CTC criteria) during treatment or to minimum and maximum value (based on normal range), will be created. A similar shift table will be provided to summarize shifts from baseline to the final post-baseline value.

Laboratory abnormalities meeting CTC criteria grade 3 and 4 will be summarized.

Laboratory abnormalities will be evaluated based on Potentially Clinically Important (PCI) criteria (criteria in PSSAP will be used first, if the criteria are not available in PSSAP, then criteria in NCI CTC will be used). For each laboratory PCI criterion, the number and percentage of subjects who have a laboratory value meeting the criteria will be summarized. Listings will be provided to summarize subject-level laboratory data for subjects meeting PCI criteria.

For the purpose of assessing for potential Hy's law cases, the frequencies and percentages of subjects with post baseline liver specific function test values that meet the following criteria of potential clinical interest will be summarized by "as treated" treatment group:

- $ALT > 3 \times ULN$
- $ALT > 5 \times ULN$
- $ALT > 10 \times ULN$
- $ALT > 20 \times ULN$
- $AST > 3 \times ULN$
- $AST > 5 \times ULN$
- $AST > 10 \times ULN$

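### SAP 10.6 summarizes DXA and body composition by visit, with no change from Screening, arm difference or confidence interval, so the paired scans go unused and attrition can mix with bone change

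*SAP*

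**What the plan says.** SAP 10.6 sets the schedule: "Dual-energy X-ray absorptiometry (DXA) is collected at screening and Week 52". It names the variables as "DXA measurements, including bone mineral density and the corresponding T-scores and Z-scores" and says that they "will be summarized by treatment group for each visit and also in" three subgroup factors, which are vitamin D status, post-menopausal status and use of a bone protective agent. Body composition, where available, is measured at the same two visits and is also summarized by arm and visit. The section names no statistic, no change from Screening, no contrast between arms and no interval.

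The neighbouring sections go further. For laboratory data, SAP 10.3 says: "The change from baseline mean, standard error, and 95% confidence interval will be presented for the mean change from baseline within each treatment group", and the same for the difference between ABBV-154 and placebo. For vital signs, SAP 10.4 says: "Mean change from baseline to each applicable post-baseline visit will be summarized for each vital sign variable", again with standard error and 95% CI within and between arms.

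No default fills the gap. SAP 10.1 gives none for DXA. Protocol 7.5 mentions mean change for laboratory and vital sign variables only and leaves further detail to the SAP. Protocol 2.2, after listing decreased bone formation among the known glucocorticoid effects, says that "HPA axis function, and bone mineral density will be closely monitored during the study".

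**The concern.** Each subject who completes both scans supplies a pair, and the change within that pair is the natural measure of bone loss or bone sparing. A table of values by arm and visit does not use the pairing. A reader who wants to know whether ABBV-154 differs from placebo must either compare arms at Week 52, which carries all of the between-subject spread, or subtract one visit's summary from the other's, which need not rest on the same people.

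The trial's rationale is to avoid the harms of long-term systemic glucocorticoids, and the background sections name osteoporotic fracture among them. Any statement about bone at the end of the study would be better supported by a contrast fixed in advance than by one derived after unblinding.

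**Working it through.** **Figures in the plan.** The documents give no BMD standard deviation, no correlation between visits and no detectable difference, so there is no stated figure to reproduce.

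**Inputs.**
- Two scans, Screening and Week 52 (SAP 10.6). The DXA row of the Activity Schedule (Protocol Appendix F), as it reads in the extracted text, is ticked at those two points and not at Premature Discontinuation.
- n = 40 per arm (SAP 2.4), an upper bound for subjects with both scans.
- Assumptions: the same standard deviation σ at both visits, and correlation r between them, shown over a range.

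**Step 1: precision.** The standard errors of the difference between two arms are:
- Week 52 values only: σ·√(2/n)
- paired change: σ·√(2(1−r))·√(2/n)
- ANCOVA on the Screening value, large samples: σ·√(1−r²)·√(2/n)

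The Week 52 standard error is therefore 1/√(2(1−r)) times that of paired change and 1/√(1−r²) times that of ANCOVA. With n = 40, the 95% half-width of the Week 52 comparison is 1.96·√(2/40) = 0.438σ.

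| r (assumed) | Week 52 ÷ paired change | Week 52 ÷ ANCOVA | Half-width, paired change | Half-width, ANCOVA |
|---|---|---|---|---|
| 0.5 | 1.00 | 1.15 | 0.438σ | 0.380σ |
| 0.8 | 1.58 | 1.67 | 0.277σ | 0.263σ |
| 0.9 | 2.24 | 2.29 | 0.196σ | 0.191σ |
| 0.95 | 3.16 | 3.20 | 0.139σ | 0.137σ |
| 0.98 | 5.00 | 5.03 | 0.088σ | 0.087σ |

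Setting 1/√(2(1−r)) = k gives r = 1 − 1/(2k²). A twofold loss against paired change thus needs r of at least 0.875, and a threefold loss at least 0.944. At r = 0.5 simple change gains nothing. ANCOVA gains at any positive r, because 1 − r² is then below 1.

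**Step 2: who is in each summary.** Let p be the fraction of an arm scanned at Screening but not at Week 52. Then:

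(Week 52 mean, subjects scanned then) − (Screening mean, all scanned) = (mean paired change in subjects with both scans) + p × (Screening mean of subjects with both scans − Screening mean of subjects without a second scan).

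The last term is composition, not bone change. It vanishes only if p = 0 or if the two groups had the same Screening mean, and it can differ between arms. This step needs no assumption about r.

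**The case against.** The other side has several sound points.

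- **The text leaves change out; it does not exclude it.** SAP 10.6 names no statistic. A reader might infer that only separate means will ever be reported, but the wording does not say that. Both scans are collected, so paired change can be derived later. What is lost is pre-specification, not data.
- **The size of the precision loss is not established.** A reader might infer that the visit-wise form is several times less precise. That needs r of roughly 0.9 to 0.95 or more, and the documents give no r.
- **Pairing does not guarantee that a small effect is seen.** A reader might infer that a one-year effect of 2 to 3% would stand out once the scans are paired. Suppose an SD of change of 4.5% and 30 subjects per arm, both assumptions. The half-width is then 1.96 × 4.5 × √(2/30) = 2.3%, so a 2% effect stays inside it.
- **Attrition is partly addressed.** Protocol 5.6 encourages subjects who stop study drug to attend the regular visits, and DXA is not among the procedures they skip. A Week 52 scan is therefore intended for them. Subjects who leave the study altogether still have none, and a paired analysis is itself limited to subjects with both scans.
- **Site mixing cannot be shown.** The summary of changes in Protocol Appendix G mentions a forearm scan when spine and hips cannot be used. A reader might infer that this shifts the visit means. The rule itself is in Operations Manual 3.6, which is not among the documents, and SAP 10.6 does not say that sites will be pooled.
- **BMD is not a listed safety measure.** Neither Protocol 3.5 nor SAP 3.4 names it. The biomarker list is redacted and bone-specific alkaline phosphatase is in the abbreviations, so DXA cannot be called the trial's sole marker of bone loss.

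These points limit the claim. They do not explain why DXA gets less than pulse rate and body temperature get in SAP 10.4, and the SAP version history records that details for the BMD analysis were added to 10.6 in version 2.0.

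**Conclusion.** The point holds as a modest gap in a descriptive safety analysis. SAP 10.6 specifies neither change from Screening nor a comparison of arms for DXA and body composition, although the same SAP specifies both, with intervals, for selected laboratory variables and for vital signs.

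Two consequences follow. First, the visit summaries can cover different subjects, so the step from one to the other can mix attrition with bone change; this rests on no assumed figure. Second, the pairing is unused. Against paired change the cost in standard error runs from none at r = 0.5 to fivefold at r = 0.98. Against ANCOVA it runs from about 1.15-fold to fivefold over the same range. The direction of the ANCOVA result holds for any positive r, given equal spread at the two visits and a large-sample approximation. The size depends on an r that the documents do not supply.

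**What to change.** In SAP 10.6, for subjects with both scans and the same skeletal site at both visits:

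- add mean (or percent) change from Screening to Week 52, with standard error and 95% CI within each arm;
- add the ABBV-154 minus placebo difference with 95% CI for each dose, in the format of SAP 10.3 and 10.4, preferably from an ANCOVA with the Screening value as covariate;
- do the same for body composition;
- keep the visit-wise table as description;
- report, per arm, how many subjects have no Week 52 scan, because the paired analysis does not cure informative dropout.

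The adjustment for the Screening value goes a step beyond what 10.3 and 10.4 ask. It is recommended because, in large samples, it does not lose precision against either alternative. The change should be made before unblinding. The cost is a few lines of SAP text and one extra table, with no new data and no effect on the primary analysis or the sample size.
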